### PFIZER CONFIDENTIAL

prescription. Multiple dispensings for the same drug on the same day should also be treated as overlapping prescriptions.

The first treatment episode for each of the treatment groups and the E+P HT group will start on the day after the index date and continue for the number of days' supply plus 90 days. If there is no consecutive prescription within the allowable 90-day gap, the treatment episode end date will be considered the 90th day after the date on which the days' supply of the patient's last dispensing ended. Follow-up will continue after the end of the first treatment episode and include subsequent treatment episodes until the subject meets a censoring criterion.

# 9.3.2. Endpoint

The endpoint is the occurrence of endometrial cancer. An algorithm for endometrial cancer will be developed and validated as part of the current study to identify the outcome in administrative claims data. The performance of endometrial cancer algorithms will be assessed for the HIRD database through medical record review and adjudication. The protocol for the validation study is included in Annex 2.

This validation component will begin after building the analytic files for the current study, identifying the cohort of patients who meet the inclusion/exclusion criteria (as described in Section 9.2 Setting), and constructing the exposure and comparator groups.

The final algorithm for endometrial cancer will be determined prior to conducting analyses to estimate and compare incidence rates of endometrial cancer for the exposure and comparator groups. The validated algorithm for endometrial cancer will be used in the HIRD. In Sweden, endometrial cancer will be identified using ICD-O-2/3-SE diagnosis codes in the Swedish Cancer Registry (Annex 1: Appendix G).

### 9.3.3. Vaginal Estrogen Use

The following drug utilization characteristics will be described during the post-index period for the vaginal estrogen exposure groups:

- Active ingredient at date of first dispensing:
  - o Estradiol vaginal
  - o Conjugated estrogen vaginal
- Formulation at date of first dispensing (vaginal cream, ring, tablet, or insert).
- Duration of use (i.e., duration of all treatment episodes combined).
- Computed for each treatment group as the sum of days in all treatment episodes.

Categorized in the HIRD and Sweden as:

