### Primary Objectives:

- 1. To estimate and compare the IR of endometrial cancer in postmenopausal women aged  $\geq$ 50 years, with a uterus, regardless of prior use of hormone therapy (defined as any estrogen, progestin, E+P HT use or other opposed estrogen hormone therapy), in the following groups:
  - a. New users of low-dose vaginal estrogen (LDVE) versus non-users of vaginal estrogen;
  - b. New users of moderate-dose vaginal estrogen (MDVE) versus non-users of vaginal estrogen;
  - c. New users of high-dose Premarin Vaginal Cream (HDVC) versus non-users of vaginal estrogen (HIRD only, as Premarin VC is not marketed in Sweden)
- 2. To estimate and compare the IR of endometrial cancer separately among the LDVE, MDVE, and HDVC new users (HIRD only) aged ≥50 years, with a uterus, and regardless of prior use of hormone therapy relative to non-users of vaginal estrogen stratified by prior use of hormone therapy including unopposed estrogen, unopposed progestin, single-entity or combination progestin-opposed estrogen therapies, other opposed estrogen hormone therapies, or no prior hormone use.
- 3. To estimate and compare the IR of endometrial cancer separately among new users of LDVE, MDVE, and HDVC (HIRD only) aged ≥50 years, with a uterus, and regardless of prior use of hormone therapy relative to non-users of vaginal estrogen stratified by duration of use, formulation, active ingredient, number of dispensings and number of dispensings per formulation.

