### 9.2.3. Post-Index Period

For new users of vaginal estrogen and E+P HT, the post-index period includes the induction period and the follow-up period. The induction period starts the day after the index date and lasts for six months or until the one of the censoring criteria (below) is met. If a censoring criterion has been met during the induction period, that subject is censored and contributes no follow-up time in the main analysis but may be included in a sensitivity analysis (see Section 9.7.4 Sensitivity Analyses). If no censoring criteria has been met during the six-month induction period, the follow-up period begins on the day after the end of the induction period. Person-time for new users of vaginal estrogen and E+P HT will only be counted during follow-up and only endometrial cancer cases occurring during follow-up will be included in the analysis as cases.

The endometrial cancer incidence rate in non-users is unrelated to treatment so the induction period does not apply to this group. Therefore, follow-up and person-time accrual for non-users begins the

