#### PFIZER CONFIDENTIAL

- Unopposed progestin
- Progestin opposed estrogen hormone therapy
- Other opposed estrogen hormone therapy
- No prior hormone therapy

Prior use of these medications will be measured using the entire baseline period.

The following subgroup analyses will be conducted separately among the PS-matched cohorts of new users of LDVE, MDVE, and HDVC and non-users of vaginal estrogens to determine if the HR of endometrial cancer varies by the following covariates (Annex 1: Tables 3 and 6):

- Active ingredient at the cohort entry date:
  - Estradiol vaginal;
  - Conjugated estrogen vaginal.
- Formulation at the cohort entry date:
  - Vaginal cream;
  - o Vaginal ring;
  - Vaginal tablet;
  - Vaginal insert.
- Duration of use.
- Number of dispensings.
- Number of dispensings per formulation

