#### PFIZER CONFIDENTIAL

- 5. HIRD only: To evaluate possible impact of missing information on medical history, we will consider extending the baseline period to 18 months. To assess if there are important differences between the populations with at least 12 months and 18 months of continuous HIRD enrollment, the HR of endometrial cancer will be calculated for LDVE users versus non-users among women who have a baseline period of at least 18 months of continuous HIRD enrollment. Comparing results using different baseline durations will assess the effect of potential misclassification of covariates and the balance with increased random error due to decreased study size (Annex 1: Table 8).
- 6. HIRD and Sweden: To determine if associations between vaginal estrogen, non-users, and E+P HT and endometrial cancer differ according to a patient's history of cancer, a sensitivity analysis will be conducted. to estimate and compare the IRs of endometrial cancer among women by history of cancer other than endometrial cancer and basal cell carcinoma (if case counts are sufficient to support estimation) in the following groups (Annex 1: Tables 9 and 13):
  - a. LDVE new users versus non-users of vaginal estrogen.
  - b. MDVE new users versus non-users of vaginal estrogen.
  - c. HDVC new users versus non-users of vaginal estrogen (HIRD only).
  - d. LDVE new users versus E+P HT new users of hormone therapy.
  - e. MDVE new users versus E+P HT new users of hormone therapy.
  - f. HDVC new users versus E+P HT new users of hormone therapy (HIRD only).
- 7. HIRD only: To identify the rate of endometrial cancer in patients who may have a cumulative exposure that is higher than the intended average daily dose, the rate of endometrial cancer will be estimated among HDVC new users compared to non-users of vaginal estrogen and HDVC new users compared to E+P HT new users stratified by number of dispensings. Number of dispensings will be categorized as ≤ 2 dispensings per year and >2 dispensings per year(Annex 1: Table 10).
- 8. HIRD only: To evaluate possible effects of dose of vaginal estrogen on risk of endometrial cancer among vaginal estrogen new users (the full study population), the HR of endometrial cancer will be calculated for HDVC new users versus LDVE new users (Annex 1: Table 10).

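### Primary Objective 3 stratifies by post-index totals of duration and dispensings, so as written its strata carry immortal-time bias and could mask harm in long-term users

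*Protocol*

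**What the plan says.** Section 8, Primary Objective 3, compares each user group with non-users "stratified by duration of use, formulation, active ingredient, number of dispensings and number of dispensings per formulation".

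Section 9.3.3 sets the measurement window: "The following drug utilization characteristics will be described during the post-index period for the vaginal estrogen exposure groups". Duration is "Computed for each treatment group as the sum of days in all treatment episodes", cut into <0.5, 0.5–<1, 1–<2, 2–<3 and ≥3 years. Section 9.2.3 states that for new users "the post-index period includes the induction period and the follow-up period". Section 9.3.1 adds: "Follow-up will continue after the end of the first treatment episode and include subsequent treatment episodes until the subject meets a censoring criterion".

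Section 9.7.3.1 then lists duration, number of dispensings and dispensings per formulation, next to active ingredient and formulation at cohort entry, as subgroup variables "to determine if the HR of endometrial cancer varies by the following covariates". The protocol nowhere mentions time-varying exposure, a landmark, or splitting person-time by use reached so far.

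On episode length, Section 9.3.1 has the first episode "continue for the number of days' supply plus 90 days"; without a further prescription inside the gap, the episode ends on the 90th day after supply runs out. In Section 9.7.4, item 7 for high-dose cream reads: "Number of dispensings will be categorized as ≤ 2 dispensings per year", with more than two per year as the other category.

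**The concern.** A total over all episodes is known only at the end of observation. Using it to place a woman in a stratum from the start of follow-up conditions on her future. A woman diagnosed early cannot accumulate three years of use, while one who does has contributed a long stretch in which no event was possible. That stretch enters the long-duration denominator. Cancers that cut use short are counted in lower categories.

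Duration-response is a direct test of an estrogen effect on the endometrium, and here it is a primary objective of a safety study. A downward distortion at the longest durations works against detecting harm where cumulative exposure is greatest.

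**Working it through.** **1. The plan's own figures.** There is no stated figure for Objective 3, so the study-size inputs (Section 9.5.1) were checked first. With HR 1.5, two-sided α 0.05, 80% power and 1:4 matching, events = (1.960 + 0.842)² / (0.2 × 0.8 × (ln 1.5)²) = 298.4, rounded up to 299 as stated (60 + 239). Exposed person-years = 0.2 × 298.4 / 0.000745 ≈ 80,104 (stated 80,105); divided by 2.4 this gives 33,377 women, as stated.

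**2. Immortal time in the top stratum.** Use is counted from the day after index; follow-up is counted after a 6-month induction. A woman with ≥3 years of use therefore has at least 3 − 0.5 = 2.5 counted years without an event.

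A closed-form check under continuous use assumes exponential censoring with the protocol's median of 2.4 years (mean 2.4 / ln 2 = 3.46) and a 13-year cap on counted follow-up. Expected follow-up after the 2.5 years is 3.46 × (1 − e^(−10.5/3.46)) ≈ 3.30 years. Events can occur only in that part, so the null rate ratio is 3.30 / (2.5 + 3.30) ≈ 0.57.

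**3. Simulation with a true HR of 1 in every stratum.** From the protocol: 74.5 per 100,000 person-years, 6-month induction, median follow-up 2.4 years, episode = supply + 90 days, and the five categories. Assumed: exponential censoring, 90-day supplies, and either continuous use (mean supplied use 0.5, 1 or 2 years) or intermittent use (probability of stopping after each dispensing 0.4, 0.2 or 0.1; mean gap 0.5 years). Rate ratios by final total:

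| Duration | Continuous: 0.5 / 1 / 2 y | Intermittent: 0.4 / 0.2 / 0.1 |
|---|---|---|
| <0.5 y | 1.00 / 0.99 / 0.99 | 1.10 / 1.26 / 1.57 |
| 0.5–<1 y | 1.05 / 1.16 / 1.42 | 1.15 / 1.47 / 1.95 |
| 1–<2 y | 0.90 / 0.95 / 1.09 | 0.86 / 1.00 / 1.21 |
| 2–<3 y | 0.68 / 0.73 / 0.82 | 0.63 / 0.68 / 0.78 |
| ≥3 y | 0.48 (17 events) / 0.57 / 0.57 | 0.45 / 0.45 / 0.44 |

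A Cox fit at an inflated event rate (continuous use, mean 1 year) gave 1.01, 1.18, 0.92, 0.73 and 0.58. Other assumed persistence and gap patterns widened the range at ≥3 years to 0.43–0.74 and the upper end at 2–<3 years to 0.90.

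**4. Number of dispensings (intermittent model).** One dispensing: 1.10–1.56. Nine or more: 0.38–0.39, and up to 0.69 under other assumed patterns.

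**5. Same data, use reached so far.** Assigning person-time and events to the duration category reached to date (continuous model) gives 0.97–1.02 in every category with adequate events; the one exception, 0.84, rests on 17 events.

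**6. Item 7.** If dispensings are annualised over observed time, an early event shortens the denominator and raises the woman's rate. Null simulations gave 0.66–0.94 for ≤2 per year and 1.7–5.9 for >2 per year (90-day supplies, stopping probability 0.1–0.4, mean gap 0–0.5 years). With assumed Poisson refills of 1–3 per year they gave 0.70–0.94 and 1.66–6.95.

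**7. Grace days.** Four isolated 30-day fills count as 4 × (30 + 90) = 480 days (1.31 years) against 4 × 30 = 120 supplied days (0.33 years), a move from <0.5 to 1–<2 years. In the intermittent model counted use is about 1.8 times supplied use, and 54% to 76% of users move up at least one category.

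**The case against.** The strongest reply is that the protocol never calls the strata fixed. Section 9.3.3 introduces the variables as descriptive, Section 9.3.1 leaves further detail on exposure definitions to the SAP, and Section 9.7 leaves detailed methodology there too. Counting-process coding is ordinary SAP content, and the SAP is not at hand. This stands as a limit: the finding concerns the analysis as the protocol writes it. It does not remove the point. The metric (a sum over all episodes, post-index), its categories and its use in the HR comparison are already set, and a general deferral does not undo them. Restricting to the first episode (Section 9.7.4, item 2) does not help, because first-episode length is also known only afterwards.

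A reader might infer more than the documents support:

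- *Risk would fall steadily with longer use.* It would not. Under continuous use the <0.5-year stratum is almost unbiased because that use ends within the uncounted induction period; the next stratum is inflated, and the strata from 2 years on are pulled down.
- *The ≥3-year bias is exactly 0.57, so a true HR of 1.75 would look null.* The protocol gives no persistence, supply length or censoring shape, so only a range is defensible.
- *Item 7 has the same bias.* It shares the use of future information, but a yearly rate does not require long survival. Annualised over observed time, the distortion runs the other way. The protocol does not state the denominator.
- *The 90-day tail creates the immortal time.* It is a separate exposure misclassification. Swedish days' supply is itself estimated, so supply-only duration is not clearly more accurate there.

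**Conclusion.** The point holds for total duration and for dispensing counts, overall and per formulation, in Primary Objective 3. With no true effect, the HRs would be roughly 0.4–0.75 at ≥3 years, 0.6–0.9 at 2–<3 years and 1.1–1.9 at 0.5–<1 year. For <0.5 year they would be near 1.0 under continuous use and up to about 1.6 under intermittent use. Sizes depend on the assumed persistence, gaps and censoring; the downward bias from 2 years on appeared in every scenario. Because events in the top stratum can occur only after three years of use, a true HR there of about 1/0.75 = 1.3 to 1/0.4 = 2.5 could appear as 1, a span that includes the 1.5 the study is powered to detect.

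Not affected: the overall user versus non-user HRs, the active-ingredient and formulation strata (set at first dispensing), and the sample size, which reproduces.

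**What to change.** - **Sections 9.3.3 and 9.7.3.1:** define cumulative duration and cumulative dispensings (total and per formulation) as time-varying exposures in the Cox model, with person-time and events assigned to the category reached so far. A landmark analysis is an acceptable alternative. Section 9.1.1 already applies this logic to non-users, whose time before starting vaginal estrogen counts as unexposed.
- **Section 9.7.4, item 7:** classify dispensing frequency from dispensings up to each time point, or within a fixed landmark window, and state the denominator.
- **Section 9.3.3, separately:** report duration with and without the 90 grace days.

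The cost is wording in three sections, counting-process data sets and slightly more programming. No new data are needed.

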#### PFIZER CONFIDENTIAL

- $\circ$  <0.5 years.
- $\circ$  0.5 to <1 year.
- $\circ \geq 1$  to <2 years.
- $\circ \geq 2$  to <3 years.
- $\circ \geq 3$  years.
- Number of dispensings.
- Number of dispensings per formulation.

### 9.3.4. Baseline Covariates

The study will identify and describe baseline covariates and prior use of estrogen and progestogen use using all available data prior to and including the index date (see Section 9.1.1 Time Periods). A continuous variable measuring the duration of use will be created for each of the following drug categories:

- Single-entity progestogen contraceptives (oral, transdermal, or injectable);
- E+P contraceptives (oral, transdermal, or injectable).
- Unopposed estrogen hormone therapy: These include oral, transdermal, and injectable singleentity estrogen medications without a progestin dispensed during the baseline period.
- Unopposed progestin hormone therapy: These include oral, transdermal, injectable, and vaginal medications without an estrogen dispensing during the baseline period.
- Progestin opposed estrogen hormone therapy: These include prior use of E+P HT study drugs and subjects who used single-entity estrogen AND single-entity progestin medications during the baseline period (the two medications' usage does not need to overlap).
- Other opposed estrogen hormone therapy: These include prior use of estrogen-testosterone combination medications, conjugated estrogen-bazedoxifene, or the use of single-entity estrogen and single-entity testosterone medications during the baseline period (the two medications' usage does not need to overlap).
- No prior estrogen or progestin hormone therapy use (not including contraceptives). This will be a binary variable indicating no prior hormone therapy use.

Prior contraceptive use may be further divided into categories for time since last dispensing:

• <6 months;

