# 8. RESEARCH QUESTION AND OBJECTIVES

What is the incidence rate (IR) of endometrial cancer in postmenopausal women with a uterus who use LDVE unopposed by progestogen compared to non-users and compared to users of estrogen-progestogen combination hormone therapy (E+P HT)?

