#### Figure 3. Cohort Selection for Primary Study Population: Vaginal Estrogen Treatment Groups and Non-Users

#### Abbreviations: HIRD, HealthCore Integrated Research Database

Vaginal estrogens include vaginal estradiol estrogen (excluding Estrace), and vaginal conjugated estrogen (Premarin Vaginal Cream, HIRD only) in low, moderate, and high doses.

Censoring date for new users is earliest of: hysterectomy, endometrial cancer, switching of treatment group study drug, dispensing of an estrogen-containing product (vaginal or non-vaginal) that does not belong to a treatment group, dispensing of a progestogen-containing product (vaginal or non-vaginal), death, disenrollment (HIRD), emigration from Sweden (Sweden), end of the study period. Censoring date for non-users is earliest of: hysterectomy, endometrial cancer, dispensing of any study drug, dispensing of an estrogen-containing product (single-entity or combination, vaginal or non-vaginal) that does not belong to a treatment group, dispensing of a progestogen-containing product (single-entity or combination, vaginal or non-vaginal), death, disenrollment (HIRD), emigration from Sweden (Sweden), end of the study period. (Sweden), end of the study period.

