#### 9.2.2. Exclusion Criteria

Patients meeting any of the following criteria will not be included in the study:

Exclusion criteria are applied to all treatment and comparator groups unless otherwise noted. Information during the baseline period is used to assess whether a subject meets the criteria unless otherwise noted (see definitions in Section 9.3 Variables). The exclusion criteria will include the following (summarized in Figure 3 above):

- Hysterectomy;
- Endometrial cancer;
- ≥1 prior dispensing of any vaginal estrogen (including study drugs and non-study drugs) prior to the index date for new users of vaginal estrogen. For non-users and E+P HT new users, this criterion will be assessed during the entire baseline period, including the potential index dates.
- $\geq 2$  dispensings of vaginal estrogen drugs on the index date that differ by strength, formulation, or active ingredient.
- Secondary analyses only:
  - $\circ \geq 1$  prior dispensing of E+P HT prior to the index date for new users of E+P HT. For vaginal estrogen users, this criterion will be assessed during the entire baseline period, including the index date;
  - $\circ \geq 1$  prior dispensing of vaginal or non-vaginal progestogen hormone therapy product (single-entity or combination, except contraceptives) not included as E+P HT study drugs.
  - ≥1 dispensing of oral, transdermal, or injectable estrogen hormone therapy product (single-entity or combination, except contraceptives) not included as E+P HT study drugs.

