### PFIZER CONFIDENTIAL

day after their index date (i.e., the date of a gynecological visit that meets all inclusion and exclusion criteria). Follow-up for all subjects will extend through the earliest of the following censoring events:

- Hysterectomy;
- Endometrial cancer;
- Dispensing of an estrogen hormone therapy product not included as a study drug (single-entity or combination, vaginal or non-vaginal formulation)
- Dispensing of a progestogen hormone therapy product not included as E+P HT (single-entity or combination, vaginal or non-vaginal formulation);
- End of continuous health plan eligibility (HIRD only);
- Emigration from Sweden (Sweden only);
- Death;
- End of the study period.
- Dispensing of a study drug that is in a different treatment group than the index treatment group, i.e., switching between LDVE, MDVE, HDVC, or E+P HT treatment groups;

Additional censoring criteria for non-users only:

• Dispensing of any study drug, which are defined in Section 9.2.1 Inclusion Criteria.

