- 4. HIRD and Sweden: The HR of endometrial cancer will be calculated without censoring on dispensing of a non-study progestogen (except contraceptives) to inform magnitude of changes on effect estimates should censoring be informative. The comparison will be done for the PS-matched LDVE users cohort versus non-users (Annex 1: Table 8 and 12).

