#### Table 3: Characteristics of Patients with Provisional Endometrial Cancer

#### PFIZER CONFIDENTIAL

Characteristic	All provisional cases	Patients with retrieved medical records	Patients whose medical records could not be obtained	Patients in the training set	Patients in the testing set
(oral, transdermal, injectable), single entity					
Estrogen hormone					
replacement therapy					
(oral, transdermal,					
injectable),					
combination, excluding					
E+P HT products					
Progestogen					
contraceptives (oral,					
transdermal, injectable,					
implant, IUD), single					
entity					
E+P contraceptives					
(oral, transdermal,					
injectable)					
E+P contraceptives					
(vaginal)					
Progestogens (oral,					
transdermal, injectable)					
Progestogens (vaginal)					
Selective estrogen					
receptor modulators					
Androgens					
Anabolic steroids					
Corticosteroids (oral					
and injectable)					
Lipid lowering agents					
Antihypertensives Antidiabetics					
Antidepressants					
Sedatives/hypnotics					
Anticonvulsants					
Antifungals					
Antivirals					
Macrolides					
Facility types					
Outpatient					

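### The protocol states conflicting censoring rules for contraceptive progestogens and leaves intrauterine and implant forms out of its baseline covariates

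*Protocol*

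**What the plan says.** Section 8 defines the population of interest as "postmenopausal women with a uterus who use LDVE unopposed by progestogen". Four parts of the protocol bear on how that condition is applied.

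- **Exclusion (Section 9.2.2).** The only progestogen exclusion is listed under the secondary analyses and exempts contraceptives: "prior dispensing of vaginal or non-vaginal progestogen hormone therapy product (single-entity or combination, except contraceptives) not included as E+P HT study drugs". The primary analysis has no progestogen exclusion.
- **Censoring.** Section 9.2.3 lists "Dispensing of a progestogen hormone therapy product not included as E+P HT (single-entity or combination, vaginal or non-vaginal formulation". Footnote 2 of Figure 3 lists, for new users, "dispensing of a progestogen-containing product (vaginal or non-vaginal), death, disenrollment (HIRD), emigration from Sweden (Sweden), end of the study period", and has a matching item for non-users. Sections 9.1.1 and 9.1.2 censor non-users when they start other non-study progestogen or progestin medication, with no mention of contraceptives.
- **Sensitivity analysis 4 (Section 9.7.4).** The hazard ratio is recalculated "without censoring on dispensing of a non-study progestogen (except contraceptives").
- **Covariates (Section 9.3.4).** Duration of contraceptive use is recorded for "Single-entity progestogen contraceptives (oral, transdermal, or injectable") and "E+P contraceptives (oral, transdermal, or injectable"). Annex 2 Table 3, which describes the validation cases, has a wider row for single-entity progestogen contraceptives that includes "implant, IUD), single" entity.

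**The concern.** The reason given for the study in Section 7 is that progestogen taken with oral estrogen lowers endometrial cancer risk. Whether a woman is also receiving a progestogen is therefore central to what the hazard ratio means. Two things follow from the text.

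First, the censoring event is part of the primary analysis. If the protocol states it in two ways, the two data partners could each follow the document and still build different risk sets.

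Second, a long-acting device is the form of progestogen that a dispensing-based rule is least able to see, and it is the form missing from the covariate definition. Users and non-users cannot be balanced on something that is not recorded.

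**Working it through.** This is a check of definitions. No stated figure in the protocol depends on it, so the texts are set side by side and applied to three women.

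**Step 1: the censoring texts.**

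| Place | Applies to | Does a contraceptive progestogen censor? |
|---|---|---|
| Section 9.2.3 | all groups | Read literally, no: only hormone therapy products are named. No express exemption is written |
| Figure 3, footnote 2 | new users and non-users | Yes: any product containing a progestogen |
| Sections 9.1.1 and 9.1.2 | non-users | Unclear: progestogen or progestin medications, on starting |
| Section 9.7.4, item 4 | LDVE users and non-users | Either reading |

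Item 4 is ambiguous for this reason. If contraceptives never censor, the exception merely describes the censoring event being lifted, and the text agrees with 9.2.3. If contraceptives do censor in the main analysis, the exception says that this censoring stays while the rest is lifted, and the text agrees with Figure 3. The study-size table in Annex 3 also excepts contraceptives, which leans towards 9.2.3, but it concerns cohort counts and not censoring.

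**Step 2: apply the rules.** By Table 1 and Section 9.2.3, follow-up of a new user starts after a six-month induction period, and a woman censored during induction contributes nothing to the main analysis. Follow-up of a non-user starts the day after index.

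- *Vaginal estrogen user, contraceptive refill in month 3 (an illustrative date).* Figure 3: censored in induction, no follow-up. Section 9.2.3 read literally: not censored, so all follow-up from the end of month 6 counts.
- *Non-user, contraceptive refill in month 3.* Figure 3: about three months of follow-up. Section 9.2.3 read literally: all of it.
- *Either group, intrauterine or implant progestogen placed before index.* Not excluded in the primary analysis. No route in 9.3.4 matches. No later dispensing arises while the device stays in place, so neither 9.2.3 nor Figure 3 censors her. She contributes all her follow-up under both rules.

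The first two cases show that the choice of rule changes the primary person-time, and does so differently in the two groups. The third shows that settling the conflict does not resolve the device question.

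**Step 3: when the device gap biases the hazard ratio.** Let p1 and p0 be the proportions of users and non-users with a device after matching, and r the endometrial cancer rate ratio under the device, taken as equal in both groups. The hazard ratio is then multiplied by

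[1 − p1(1 − r)] / [1 − p0(1 − r)].

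If p1 = p0 the factor is exactly 1. If r is below 1 and p1 exceeds p0 the factor is below 1; if p0 exceeds p1 it is above 1. The protocol gives none of p1, p0 or r. Section 7 concerns progestogen taken with oral estrogen and supplies no device effect, so no number can be put in from the documents.

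**The case against.** Several counter-arguments have force.

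- **Most contraceptives are measured.** Oral, transdermal and injectable forms have duration variables in 9.3.4, with optional recency categories, and 9.7.1 lets the propensity score draw on medication use. A reader might infer that all women on contraception are unmeasured and unbalanced. The text does not support that; the gap is confined to intrauterine and implant forms.
- **The code lists are not shown.** Annex 1 Appendix D-3 covers progestin contraceptives and may contain device codes, and the protocol leaves propensity score detail to the SAP. So it cannot be said that devices will certainly go unseen. What stands is that the written definition in 9.3.4 names three routes and Annex 2 names more. The conflicting censoring rules are both in the protocol and are not detail left for later.
- **A bias analysis is already planned.** Item 9 of Section 9.7.4 addresses misclassified prior use of progestogen-containing products for LDVE. This is a real safeguard, though it names neither contraceptives nor devices.
- **Menopausal status.** A reader might infer that age 50 alone stands for menopause. For the exposed groups, Section 9.2.1 also restricts study drugs to products approved only for vulvar and vaginal atrophy due to menopause. An added age restriction would be a preference, not a correction.
- **New codes will not find every device.** The HIRD look-back can be as short as 12 months, and Section 9.4.2 says the Swedish drug register misses drugs administered in hospital or in specialised outpatient care. This limits what the covariate can achieve, and is why the bias analysis should name devices.

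**Conclusion.** The point holds in two limited parts. The censoring rule for contraceptive progestogens is stated inconsistently, and the choice alters person-time in the primary analysis. Intrauterine and implant progestogens, as defined in 9.3.4, are not available to the propensity score, and neither censoring rule catches a device already in place at index.

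The size is unknown. Confounding of the hazard ratio requires that device use still differ between groups after matching, and the direction depends on which group has more of it. With equal use there is no confounding under the assumption in Step 3, although the affected women are still not using estrogen unopposed. It would be going too far to infer a hazard ratio bias of any particular size: that would need assumed prevalences and an assumed device effect, for which the documents give no basis. A blanket exclusion of recent contraceptive users does not follow either, since most of that use is recorded and can be adjusted for.

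**What to change.** 1. State one censoring rule for contraceptive progestogens that covers all routes, including insertion of a device during follow-up. Use it in identical words in Sections 9.1.1, 9.1.2 and 9.2.3, Figure 3 and item 4 of Section 9.7.4, and apply it in both databases.
2. Add intrauterine and implant progestogens to the covariates in 9.3.4 and to the propensity score candidates, using dispensing and insertion codes over all available look-back.
3. Name uncaptured devices in the quantitative bias analysis (Section 9.7.4, item 9), because the look-back and the Swedish drug register will miss some.

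The cost is extra drug and procedure codes and, if contraceptive dispensings are made to censor, slightly less person-time. For LDVE in the HIRD there is room: 152,941 expected users against 33,377 required, about 4.6 times as many (152,941 / 33,377). That margin should not be assumed elsewhere: the protocol expects that the Swedish MDVE group may be small and gives no size for HDVC. The changes are best made before the cohorts are built.
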